I. Study Design

- a. Prospective, noninvasive study to examine the individual and combined effects of OMT and Bio Electro-Magnetic Regulation (BEMER) Therapy on low back pain in adults.
- b. Study treatment location: All treatments and post treatment measurements will be performed in the osteopathic manipulative therapy laboratory at Lake Erie College of Osteopathic Medicine, Bradenton. [name] or [name], who are licensed osteopathic physicians, will be on call in the vicinity of the treatment location, however not necessarily in the room of treatment.
- c. Data Collection
 - i. After written consent is obtained, the study coordinator will assign the participant a randomized study number to de-identify the participant.
 - ii. To achieve our project's goal, we will have 4 separate groups (OMT, BEMER, OMT+BEMER, and Placebo). OMT, BEMER, and placebo treatments will be performed by osteopathic medical students who have completed additional training given by a licensed osteopathic physician, to ensure uniform technique.
 - iii. To control for anchoring bias, subjects will be randomized into one of the four groups: OMT, BEMER, OMT+BEMER, and Placebo.
 - iv. Osteopathic Manipulation Diagnosis and Treatment Protocol

Osteopathic Diagnosis and Screening

1. Observe and Palpate Thoracic and lumbar muscles for TART (tenderness, asymmetry, restriction of motion, and tenderness) changes
2. Lumbar intersegmental diagnosis: used to guide treatment with muscle energy technique
3. Counterstrain Tenderpoint screening for the following muscles: psoas major, quadratus lumborum and piriformis- used to guide treatment with counterstrain technique
4. Sacrum diagnosis: Spring test at the base of the sacrum for palpation of flexed or extended dysfunction
5. Sacroiliac dysfunction: ASIS compression test – used to lateralize somatic dysfunction at sacroiliac joints

Osteopathic Treatment/Techniques

6. Regional thoracic myofascial release technique prone
7. Lumbosacral fascia myofascial release technique prone
8. Lumbar soft tissue unilateral pressure technique prone
9. Lumbar muscle energy technique seated or lateral recumbent

10. Psoas, piriformis, quadratus lumborum counterstrain technique supine
11. Sacrum balanced ligamentous tension technique supine
12. Lumbosacral/Pelvic fascia Myofascial Release technique supine

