 - i. The study duration is three weeks. The subjects will be required to have either OMT, BEMER, OMT+BEMER, or Placebo treatments during the course of the study. Each subject in the OMT groups (i.e. OMT and OMT+BEMER) will receive treatment 3 times per week for a period of 3 weeks. Subjects in the BEMER groups (i.e. BEMER and OMT+BEMER) will receive treatment 5 times per week for a period of 3 weeks. Finally, subjects in the Placebo group will receive the light touch and BEMER sham treatments at same intervals as the corresponding experimental groups. OMT, BEMER, and placebo treatments will be performed by osteopathic medical students who have completed additional training given by a licensed osteopathic physician, to ensure uniform technique.
- b. Recruitment:

- i. LECOM-Bradenton faculty, staff, osteopathic medical, dental, pharmacy, and master's students will be informed via email of the opportunity to participate in the research study and will be given contact information to confirm eligibility with a study coordinator (Appendix A).

c. Experimental Sessions

- i. Following written consent (Appendix B), subjects will be given a randomized study ID number. They will be randomized into their treatment group.
- ii. Each subject in the OMT groups (i.e. OMT and OMT+BEMER) will receive treatment 3 times per week for a period of 3 weeks. As previously mentioned, subjects in the BEMER groups (i.e. BEMER and OMT+BEMER) will receive treatment 5 times per week for a period of 3 weeks. Finally, subjects in the Placebo group will receive the light touch and BEMER sham treatments at same intervals as the corresponding experimental groups. OMT, BEMER, and placebo treatments will be performed by osteopathic medical students who have completed additional training given by a licensed osteopathic physician, to ensure uniform technique. All treatments will be performed during the span of three consecutive weeks.
- iii. Subjects will complete brief questionnaires regarding low back pain and quality of life before the beginning of study and will complete the same questionnaires following the completion of the three week treatment (Appendices C, D, E).

III. Analysis

a. Study Statistics

- i. Primary outcome variable
 1. Questionnaire ratings before and after treatments
- ii. Statistical plan including sample size justification and interim data analysis
 1. Paired T-tests (N~10 subjects) to investigate the changes in low back pain after each treatment protocol.

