 2. One-Way ANOVA to investigate any statistically significant differences between the means of each of the 4 experimental groups.
- iii. Early stopping rules
 1. Any adverse effect, as determined by the attending licensed osteopathic physician. No adverse effects are anticipated.

b. Blinding

- i. All outcome analyses will be performed in a blinded fashion. Subject survey and corresponding data will be de-identified and analyzed retrospectively by investigators with no exposure to the treatment sessions. Doing so will eliminate bias associated with investigator self-interest and ensure subject anonymity.

IV. Drugs/Substances/Devices

- a. Drugs will not be used in this trial. Instead, subjects will be given osteopathic manipulative treatment, BEMER therapy, and placebo light touch.
- b. The device utilized is BEMER Pro set.

Research Participants

The target population is LECOM-Bradenton faculty, staff, osteopathic medical, dental, pharmacy, and master's students who are currently experiencing low back pain. The study will not target participants from a vulnerable or at-risk population. Our target population will be informed via email of the opportunity to participate in the research study and will be given contact information to confirm eligibility with a study coordinator.

I. Inclusion

- a. LECOM-Bradenton faculty, staff and Students currently enrolled in LECOM-Bradenton's osteopathic medical program, pharmacy program, dental program, and master's program who are currently experiencing low back pain will be approached for recruitment.

II. Exclusion

- a. Subjects will be excluded if they are unable to provide informed consent, are currently pregnant, or have a known medical history of current
 - i. Psychiatric conditions
 - ii. Skin disorders or open wounds precluding skin contact
 - iii. Fasciitis or fascial tears
 - iv. Myositis
 - v. Neurological symptoms such as numbness, tingling, weakness in lower extremities
 - vi. Neoplasia
 - vii. Cancer
 - viii. Bone fracture, osteomyelitis, or osteoporosis
 - ix. Coagulation problem
 - x. Deep vein thrombosis
 - xi. Adrenal diseases/syndromes
 - xii. Acute upper or lower respiratory infection
 - xiii. Immunosuppressive syndromes
 - xiv. Radiation or chemotherapy within the past 3 years
 - xv. Lupus
 - xvi. Osteopenia
 - xvii. Congestive heart failure
 - xviii. BMI greater than 30
 - xix. Any other autoimmune disease not stated above
 - xx. Medication changes within the last 4 weeks

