Appendix C:
SF-12 Health Survey

SF-12 HEALTH SURVEY (STANDARD)

INSTRUCTIONS: This questionnaire asks for your views about your health. This information will help keep track of how you feel and how well you are able to do your usual activities.

Please answer every question by marking one box. If you are unsure about how to answer, please give the best answer you can.

1. In general, would you say your health is:

				
Excellent	Very good	Good	Fair	Poor

The following items are about activities you might do during a typical day. Does your health now limit you in these activities? If so, how much?

	Yes, Limited A Lot	Yes, Limited A Little	No, Not Limited At All
2. Moderate activities , such as moving a table, pushing a vacuum cleaner, bowling or playing golf			
3. Climbing several flights of stairs			

During the past 4 weeks, have you had any of the following problems with your work or other regular daily activities as a result of your physical health?

	Yes	No
4. Accomplished less than you would like		
5. Were limited in the kind of work or other activities		

During the past 4 weeks, have you had any of the following problems with your work or other regular daily activities as a result of any emotional problems (such as feeling depressed or anxious)?

	Yes	No		
6. Accomplished less than you would like				
7. Didn't do work or other activities as carefully as usual				
8. During the past 4 weeks , how much did pain interfere with your normal work (including both work outside the home and housework)?				
				
				
				
Not at all	A little bit	Moderately	Quite a bit	Extremely

These questions are about how you feel and how things have been with you during the past 4 weeks. For each question, please give the one answer that comes closest to the way you have been feeling. How much of the time during the past 4 weeks –

[figure not shown]

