Appendix D:

Visual Analog Scale

The Visual Analog Scale (VAS) is a 100-millimeter line with “no pain” on one end and “pain as bad as it can be” at the other end. This scale is a very simple form of assessment. Patients are expected to mark on the line the amount of pain they are experiencing.

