Appendix E: Oswestry low back pain questionnaire

Instructions

This questionnaire has been designed to give us information as to how your back or leg pain is affecting your ability to manage in everyday life. Please answer by checking ONE box in each section for the statement which best applies to you. We realise you may consider that two or more statements in any one section apply but please just shade out the spot that indicates the statement which most clearly describes your problem.

section 1 - pain intensity

- I can tolerate the pain I have without having to use pain killers
- the pain is bad but I manage without taking pain killers
- pain killers give complete relief from pain
- pain killers give moderate relief from pain
- pain killers give very little relief from pain
- pain killers have no effect on the pain and I do not use them

section 2 - personal care (washing, dressing, etc)

- I can look after myself normally without causing extra pain
- I can look after myself normally but it causes extra pain
- it is painful to look after myself and I am slow and careful
- I need some help but manage most of my personal care
- I need help every day in most aspects of self care
- I do not get dressed, wash with difficulty and stay in bed

section 3 - lifting

- I can lift heavy weights without extra pain
- I can lift heavy weights but it gives extra pain
- pain prevents me from lifting heavy weights off the floor, but I can manage if they are conveniently positioned, eg on a table
- pain prevents me from lifting heavy weights but I can manage light to medium weights if they are conveniently positioned
- I can lift only very light weights
- I cannot lift or carry anything at all

section 4 - walking

- pain does not prevent me walking any distance
- pain prevents me walking more than 1 mile
- pain prevents me walking more than 1/2 mile
- pain prevents me walking more than 1/4 mile
- I can only walk using a stick or crutches
- I am in bed most of the time and have to crawl to the toilet

section 5 - sitting

- I can sit in any chair as long as I like
- I can only sit in my favourite chair as long as I like
- pain prevents me from sitting more than 1 hour
- pain prevents me from sitting more than 1/2 hour
- pain prevents me from sitting more than 10 minutes
- pain prevents me from sitting at all

section 6 - standing

- I can stand as long as I want without extra pain
- I can stand as long as I want but it gives me extra pain

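### The primary outcome covers three questionnaires and names no primary score, so between-arm testing alone carries about a 9% to 14% false-positive chance instead of 5%

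*Combined protocol and SAP*

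**What the plan says.** Section III.a.i (Primary outcome variable) has one entry: "Questionnaire ratings before and after treatments". Section II.c.iii (Experimental Sessions) shows which questionnaires are meant. Subjects fill them in before the study and "will complete the same questionnaires following the completion of the three week treatment (Appendices C, D, E").

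The three appendices are:
- Appendix C: the SF-12, a 12-item general health survey.
- Appendix D: a single pain rating. "The Visual Analog Scale (VAS) is a 100-millimeter line".
- "Appendix E: Oswestry low back pain questionnaire", with ten sections.

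No scoring rule is given for the SF-12 or the Oswestry.

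Section III.a.ii then lists two analyses and calls neither of them primary:
- "Paired T-tests (N~10 subjects) to investigate the changes in low back pain after each treatment protocol"
- "One-Way ANOVA to investigate any statistically significant differences between the means of each of the 4 experimental groups"

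The first is limited to low back pain. The second names no outcome. No alpha, ranking of scores or multiplicity rule appears in the sections reviewed. The consent form (Appendix B) was not available, and nothing elsewhere points to it for an outcome definition.

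**The concern.** A primary outcome is meant to fix, before the data are seen, which result answers the trial's question. Here the plural wording takes in every questionnaire. With three instruments and no order among them, the investigators could report as primary whichever scale reaches significance without departing from the text. Each additional score is another chance of a false positive.

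This holds even if only the between-arm ANOVA is used, so it is distinct from the question of whether within-arm before-after tests can show a treatment effect. At stake is whether a positive claim for OMT, BEMER or the combination can be read at any stated error rate.

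**Working it through.** **Inputs**
- Arms: 4 (I.c.ii and iii, Study Design).
- Subjects per arm: about 10 (III.a.ii.1). The budget agrees: 4 × 10 = 40, and $2,000 / $50 = 40.
- Instruments: 3 (Appendices C, D, E). One score each is assumed. The SF-12 might yield two, which would make 4 scores.
- Alpha: not stated. Assumed two-sided 0.05 per test, unadjusted.
- Correlation between scores: not stated. Taken over the range 0 to 0.9.

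The plan gives no power or error-rate figure to reproduce. Its sample size cannot be rebuilt either, because effect size, standard deviation, alpha and power are all absent.

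**Step 1: independent scores, one ANOVA each.** The chance of at least one false positive among k tests is 1 − (1 − 0.05)^k.
- k = 1: 5.0%
- k = 2: 1 − 0.95² = 9.8%
- k = 3: 1 − 0.95³ = 14.3%
- k = 4: 1 − 0.95⁴ = 18.5%

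**Step 2: correlated scores, one ANOVA each.** Scores from the same subject will be correlated, which lowers these figures. The simulation used 4 arms of 10, multivariate normal change scores, no effect in any arm, and 40,000 runs per setting. Entries are the chance of at least one ANOVA with p < 0.05.

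| Scores tested | r = 0 | r = 0.3 | r = 0.5 | r = 0.7 | r = 0.9 |
|---|---|---|---|---|---|
| 2 (VAS, Oswestry) | 10.1% | 9.7% | 9.4% | 8.4% | 7.3% |
| 3 (one per instrument) | 14.1% | 13.7% | 12.9% | 11.4% | 8.7% |
| 4 (SF-12 as two scores) | 18.6% | 17.6% | 16.2% | 13.7% | 9.5% |

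A single ANOVA on one score gave 4.8% to 5.1% in the three-score runs.

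**Step 3: adding the within-arm paired t-tests.**
- One score, four paired tests plus one ANOVA: about 19%.
- Paired tests on the VAS and Oswestry (2 × 4 = 8 tests) plus ANOVAs on all three scores: about 28% at r = 0.9 to 38% at r = 0 (20,000 runs). A 40,000-run repeat gave 27.1% and 38.0%, so the lower end is good to about one point.
- Paired tests on all three scores (3 × 4 = 12 tests) plus three ANOVAs: 31% at r = 0.9 to 47% at r = 0.

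These assume no mean change in any arm. Natural recovery or placebo response would make the paired tests significant more often still, without any treatment effect.

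**Step 4: separating the two sources.** With between-arm tests only, leaving the score unnamed moves the rate from 5% to about 9–14%. With one named score, the paired tests alone move it from 5% to about 19%. The larger totals in Step 3 mix the two, and most of the increase comes from the paired tests.

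**Step 5: after the change.** One named score and one between-arm test: 5%. If all three scores stayed primary, Bonferroni at 0.05 / 3 = 0.0167 per ANOVA would give 1 − (1 − 0.0167)³ = 4.9% if independent. Either figure holds only if the paired tests are secondary or are included in the adjustment.

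**The case against.** The strongest reply is that the plan already points to its target. The paired-test line is confined to low back pain, II.c.iii distinguishes low back pain from quality of life, and the SF-12 is a general health survey. This stands in part: the text does not clearly put the SF-12 into the paired tests. It still leaves both the VAS and the Oswestry, and the ANOVA line names no outcome. On this narrow reading the between-arm rate is about 7% to 10%, which is a smaller excess over 5% but still an excess.

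A second reply is that the 5% benchmark is not the plan's own. That is correct. It is an assumption, and the missing alpha is part of the same gap.

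A third is that section III.b promises blinded outcome analysis. Concealing arm labels does not stop the choice of which scale to feature once the p-values are known.

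Two stronger readings are tempting. A reader might infer that leaving the score unnamed by itself produces a false-positive rate of 40% or more. Such figures need within-arm tests on the SF-12 as well, which the text does not clearly plan, and they come mostly from the within-arm tests. A reader might also infer that the plan declares any significant test to be a primary success. It contains no such rule; it simply does nothing to exclude that use.

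**Conclusion.** The concern holds on every reading of the text. The primary outcome is not reduced to one score, and nothing in the plan controls the error rate across scores. The size attributable to this point is about 9% to 14% with one ANOVA per instrument, or about 7% to 10% if only the VAS and Oswestry count, against 5% for one named score. This rests on an assumed two-sided 0.05 per test, 10 subjects per arm, normal change scores and correlations from 0 to 0.9. The independence figure of 14.3% is an upper value for three scores and should not be quoted as exact.

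The higher totals, about 28% to 38% and up to 47% if the SF-12 is also tested within arms, show what the whole plan allows. They should not be charged to the unnamed score alone.

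It would also go too far to say that the documents single out the VAS. The title and aim concern low back pain, but Appendix D asks about pain without mentioning the back, and it is Appendix E whose title does.

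**What to change.** In section III.a, before any data are analysed:
1. Name one low back pain score as the primary outcome. It could be the VAS, with Appendix D reworded to ask about low back pain, or the Oswestry with its scoring stated. The choice is the investigators'.
2. Name one between-arm comparison of that score after the three-week treatment, at two-sided 0.05, as the primary analysis. Say whether change or the post-treatment value is compared. If the comparison is the four-arm ANOVA, the 5% covers that overall test only, so claims about a particular arm need their own stated rule.
3. Make the other questionnaires and all within-arm paired t-tests secondary and descriptive, reported with confidence intervals, or Holm-adjusted if significance is claimed.

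The cost is a few sentences in III.a, plus a wording change in Appendix D if the VAS is chosen. No further subjects or visits are needed. The small downside is that an effect appearing only on a secondary scale can no longer be presented as the primary result.

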Title: Effects of Osteopathic Manipulative Treatment and Bio Electro-Magnetic Regulation Therapy on Low Back Pain in Adults.

NCT04704375

June 13, 2019

Principal Investigator:

[name]., M.S., M.S. (Med Ed)
Lake Erie College of Osteopathic Medicine, Bradenton Florida
[contact]
Email: [contact]

Research Title:

Effects of Osteopathic Manipulative Treatment (OMT) and Bio Electro-Magnetic Regulation (BEMER) Therapy on low back pain in adults.

Research Purpose:

The aim of this project is to investigate the individual and combined effects of Osteopathic Manipulative Treatment (OMT) and Bio Electro-Magnetic Regulation (BEMER) Therapy on low back pain in adults.

Study Summary:

It is clear that low back pain (LBP) is a major challenge in our society, which can lead to severe disability in many individuals. Although there are several different treatments and approaches to help individuals with LBP, the number affected by this condition has been steadily increasing.

OMT has been shown to be helpful in the treatment of LBP. In fact, the use of OMT has been shown to increase mobility of the lumbar myofascial tissues, visceral motion and decrease pain in patients with LBP. Bio Electro-Magnetic Regulation (BEMER) Therapy is a therapeutic modality that deploys a biorhythmically defined stimulus through a Pulsed Electromagnetic Field (PEMF), which leads to an increase in blood flow. The positive effects of BEMER on the circulation has been shown to result in significant increases in arteriovenous oxygen difference, number of open capillaries, arteriolar and venular flow volume, and flow rate of red blood cells in the microvasculature [1, 2]. Therefore, BEMER can potentially be used in the treatment of LBP by improving microcirculation in muscular tissue. In fact, BEMER with physiotherapy showed reductions in pain and fatigue acutely in patients with chronic low back pain [3]. A systemic review of randomized controlled trials that investigated whether PEMF was effective in low back pain showed there was decrease in pain intensity and improved functionality in individuals with different low back pain conditions [4].

Therefore, it is plausible that the combination of OMT and BEMER therapy may help increase circulation to myofascial structures that influence low back restriction and pain. The purpose of

this study is to investigate the individual and combined effects of OMT and BEMER therapy on low back pain.

Review of Literature:

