1. BEMER is a therapeutic modality that deploys a biorhythmically defined stimulus through Pulsed Electromagnetic Field (PEMF). This stimulus has a targeted effect on the microvasculature, and the primary effect is an improvement in tissue microcirculation [3]. The positive effects of vasomotion on the microcirculation has been shown to result in significant increases in arteriovenous

oxygen difference, number of open capillaries, arteriolar and venular flow volume, and flow rate of red blood cells in the microvasculature [1, 2]. Therefore, BEMER can potentially be used in the treatment of LBP by improving microcirculation in muscular tissue.

- iii. Placebo (Light touch, and BEMER Sham): Treaters will place their hands lightly on the subject's lumbar paraspinal muscles in the supine and prone positions in the same area as where one would place your hands for lumbar MFR technique for the same amount of time as it would take to perform MFR in this area (approximately 5 minutes). However, no lifting or action will be done. In addition, the subject will lie down on the BEMER mat (as they would do during a BEMER session), but the device will not be activated. This treatment will be used as a control.
- e. The research assistants will individually coordinate experimental times with the subjects. A licensed osteopathic physician will be in the vicinity of the treatment location at all times while treatments are being given.
- f. OMT, BEMER, and placebo will be performed by osteopathic medical students who have completed additional training given by a licensed osteopathic physician to ensure uniform technique. A licensed osteopathic physician will be in the vicinity of the treatment location at all times while treatments are being given.
- g. All data collection logs will be de-identified of personal information and only contain the randomized participant ID number linking the participant to the data collected. [name], who is one of the research coordinators, will be the data analyst.
- h. The identifying information will be maintained by the principal investigator in a locked cabinet, which he alone has access to.

II. Study Procedures and Timeline

- a. Study duration

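### No test is named to decide efficacy: the within-arm paired t-tests ignore Placebo, and the omnibus ANOVA does not show which arm differs from it

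*Combined protocol and SAP*

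**What the plan says.** The whole statistical plan stands in Methodology, III. Analysis, a.ii. Item 1 is "Paired T-tests (N~10 subjects) to investigate the changes in low back pain after each treatment protocol". Item 2 is "One-Way ANOVA to investigate any statistically significant differences between the means of each of the 4 experimental groups". The primary outcome, in III.a.i, is only "Questionnaire ratings before and after treatments", with no instrument named. Section II.c.iii refers to Appendices C, D and E, which hold the SF-12, a 100 mm VAS for pain and the Oswestry questionnaire.

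The design is comparative. Under I.c.iii, "subjects will be randomized into one of the four groups: OMT, BEMER, OMT+BEMER, and Placebo". Of the light-touch and sham-mat treatment, section I.d.iii says "This treatment will be used as a control". The Research Purpose is to "investigate the individual and combined effects of Osteopathic Manipulative Treatment (OMT) and Bio Electro-Magnetic Regulation (BEMER) Therapy on low back pain in adults".

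The supplied text gives no contrast of an active arm with Placebo, no contrast of the combination with a single modality, no follow-up to the ANOVA, no multiplicity rule, no significance level and no statement of which item carries the efficacy conclusion.

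**The concern.** A before-after test within one arm mixes any treatment effect with natural recovery, regression to the mean and placebo response. All three are plausible here. Under Research Participants, I. Inclusion, people "who are currently experiencing low back pain will be approached for recruitment", with no minimum duration of pain. The Review of Literature says that new episodes may resolve quickly, although many cases persist.

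Item 1 applies to each treatment protocol, so Placebo probably gets its own paired test. That invites the reading that an arm works because it is significant and Placebo is not. This pattern does not test the difference between the arms.

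Item 2 uses the randomisation, and shared recovery does not bias it. But it is an omnibus test. Its input is not stated (change or post-treatment score, and which questionnaire), and on post-treatment scores it makes no use of baseline.

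A significant paired test beside a non-significant ANOVA is not a contradiction, because the two answer different questions. Without a stated rule, however, the investigators can choose after seeing the results which one carries the claim.

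**Working it through.** **Inputs from the documents.** Four arms (Methodology I.c.ii), about 10 subjects per paired test (III.a.ii.1), and an estimated 40 subjects in the budget (Payment and Costs, II). 4 × 10 = 40, so the two figures agree. The sample size of 10 cannot itself be reproduced, because no significance level, power, effect or SD is given.

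**Assumptions.** Equal allocation, two-sided 5%, normal scores, all subjects complete. There is no treatment effect: every arm, Placebo included, improves by the same d, in SDs of the change score.

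**1. One paired test.** With n = 10 (9 df) the critical value is 2.262 and the noncentrality is d√10. Let p be the probability of a significant improvement in one arm. The arms are independent, so:
- at least one of three active arms significant: 1 − (1 − p)³
- at least one active arm significant and Placebo not: (1 − p)[1 − (1 − p)³]

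| d | p | any active arm | active but not Placebo |
|---|---|---|---|
| 0.3 | 0.134 | 0.350 | 0.303 |
| 0.5 | 0.293 | 0.646 | 0.457 |
| 0.8 | 0.616 | 0.944 | 0.362 |
| 1.0 | 0.803 | 0.992 | 0.195 |

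For d = 0.5: (1 − 0.293) × 0.646 = 0.457. At 0.8 to 1.0 SD, Placebo is itself significant in 62% to 80% of trials, which is a visible warning.

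**2. Paired tests beside the ANOVA (simulation).** Under the same shared recovery the ANOVA rejects in 4.9% to 5.1% of trials, on change or post-treatment scores. The active-but-not-Placebo pattern together with a non-significant change-score ANOVA occurs in 27%, 43%, 34% and 18% of all trials for the four values of d.

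**3. Two pain scores.** Section II.c.iii says "Subjects will complete brief questionnaires regarding low back pain and quality of life before the beginning of study", which separates pain from quality of life. If item 1 is read as covering VAS and Oswestry in all four arms, there are 2 × 4 = 8 paired tests. With an assumed correlation of 0.5 between the two changes, the active-but-not-Placebo pattern appears on at least one score with probability 0.477, 0.655, 0.529 and 0.311. With no change in any arm, at least one of the 8 tests is significant in 32% of trials (30% to 33% for correlations 0.7 to 0.3). False improvement in an active arm occurs in 13% (12% to 14%).

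**4. What the omnibus F can say.** The noncentrality is 10 Σ(mᵢ − m̄)². It equals 10 × 0.75 × δ² both when one active arm alone differs by δ from the other three groups and when all three active arms differ by δ from Placebo. Power is therefore the same in both cases: 17%, 38% and 57% at δ = 0.5, 0.8 and 1.0 SD. If two active arms differ from Placebo by +0.7 and −0.7 SD and the third equals it, power is 70%. A significant F separates none of these cases. Following it with three unadjusted contrasts against Placebo would carry a family-wise error of about 12%.

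**5. The alternative.** With the post-treatment score adjusted for baseline, Dunnett contrasts of three arms with Placebo have critical value 2.454 (35 df). Under shared recovery any contrast is significant in 4.9% to 5.1% of trials, and false improvement occurs in 2.4% to 2.6%.

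**The case against.** The strongest reply is that the two items have different purposes. Item 1 describes change within each arm. Only item 2 speaks of differences between groups, and Placebo is one of those groups. On that reading the ANOVA is the comparison, it holds its 5% error rate, and what is missing is its input score and its follow-up contrasts. The large percentages above then describe a misreading that the plan never states as a rule. The 8 tests also rest on an inference about which questionnaires and arms item 1 covers.

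Part of this stands. The ANOVA is valid, and the percentages measure a risk of misuse, not an error rate of the between-arm test. But the plan does not say that item 2 decides, and the only stated sample size is attached to item 1. Even if item 2 decides, the plan followed exactly cannot say whether OMT, BEMER or the combination differs from Placebo.

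Three further points are fair:
- Research Participants, III removes non-adherent subjects and those with adverse effects. Session frequency differs by arm, so removal could differ too and weaken any between-arm test. The error rates above assume complete data.
- The two combination contrasts proposed below give about 9% false positives if tested unadjusted.
- The unnamed instrument is a defect in its own right. The present point does not depend on it.

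That the study is small does not answer the point: it plans significance tests, and its aim is about the effects of treatment.

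**Conclusion.** The concern holds and should be fixed before the data are analysed. That the plan names no deciding test and has no contrast with Placebo or for the combination follows from the text alone and needs no assumption. The size is illustrative: with no true effect and one score, the misleading within-arm pattern arises in about 20% to 46% of trials for shared improvements of 0.3 to 1.0 SD, against about 5% for a between-arm test. It peaks at moderate recovery and falls when recovery is large enough for Placebo to be significant as well. These figures rest on the assumed recovery sizes, 10 complete subjects per arm and two-sided 5% tests.

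**What to change.** Amend III.a before the data are analysed:

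- Name one low back pain score, VAS or Oswestry, as primary.
- Make the between-arm comparison the efficacy analysis: post-treatment score adjusted for baseline, with prespecified contrasts of OMT, BEMER and OMT+BEMER each against Placebo, under Dunnett or Holm control.
- List OMT+BEMER against OMT alone and against BEMER alone as secondary contrasts. State their multiplicity rule or label them exploratory.
- Report within-arm changes with 95% confidence intervals as descriptive only.

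No new data or visits are needed. The cost is fewer nominally significant results and low power, which the plan should state. At 10 per arm, the true difference from Placebo needed for 80% power is:

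| Analysis | Difference |
|---|---|
| Two-group t-test, unadjusted (18 df) | 1.32 SD |
| Two-group t-test, Bonferroni over three (18 df) | 1.57 SD |
| Bonferroni, pooled SD (36 df) | 1.51 SD |
| Dunnett, pooled SD (36 df), no baseline | 1.48 SD |
| Dunnett with baseline, before-after correlation 0.3 / 0.5 / 0.7 | 1.44 / 1.30 / 1.08 SD |

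The SD is that of the score analysed; in the last row it is that of the post-treatment score. The correlations are assumed, since the documents give none. At a correlation of 0.5, power is 13%, 35% and 54% for true differences of 0.5, 0.8 and 1.0 SD.

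A design limit remains. Placebo receives light touch plus the inactive mat, while no sham of the other modality is described for the single-modality arms. These contrasts may therefore not remove all placebo response, and the report should say so.
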